### 7.2 Analyses of Secondary Objectives of Immunogenicity

HAI antibody titers specific for each of the virus strains will be assessed in terms of GMT, GMR, SCR, and SPR (HAI only) at Days 0, 28, 56, 182, and 364. Derived/calculated endpoints based on these data will include:

- Geometric mean titer (GMT) – defined as the antilog of the mean of the log-transformed HAI titers on Days 0, 28, 56, 182, and 364.

- Geometric mean ratio (GMR) – defined as the ratio of post-vaccination to pre-vaccination HAI GMTs ( $GMR_{Post/Pre}$ ) on Days 28, 56, 182, and 364.

- Within-group geometric mean ratio ( $GMR_{post/pre}$ ) for each arm will be conducted using paired t distribution. A sample SAS code is given below:

```
proc ttest data= fludata alpha=0.05;
  by Group Visit;
  PAIRED log(HAI_D28)*log(HAI_D0);
run;
```

- Seroconversion rate (SCR) – defined as proportion of subjects with either a baseline reciprocal (Day 0) titer of < 10 and a post-vaccination reciprocal titer  $\geq 40$ , or a baseline reciprocal (Day 0) titer of  $\geq 10$  and a post-vaccination titer  $\geq 4$ -fold higher on Days 28, 56, 182, and 364.

- SCR and corresponding 2-sided exact binomial 95% CIs will be calculated using the Clopper-Pearson method with the following sample SAS code:

```
proc freq data=fludata noprint;
  by treatment;
  tables seroconvind / binomial(exact) alpha=.05;
  output out=out1 binomial;
run;
```

- Pearson Chi-Square p-value will be derived for testing the equality of SCRs between two groups; otherwise Chi-Square p-value will be derived with continuity adjustment if small sample size. The Newcombe method will be used to construct its 95% confidence interval with the following sample SAS code:

```
proc freq data = fludata noprint;
  tables trt*seroconvind / riskdiff (column=2 cl=(newcombe))
  chisq;
run;
```

- Seroprotection rate (SPR) – defined as the proportion of subjects with a reciprocal HAI titer  $\geq 40$  on Days 28, 56, 182, and 364 (HAI only). SPR and corresponding 2-sided exact binomial 95% CIs will be constructed similarly using the Clopper-Pearson method. Chi-Square p-value will be derived for testing the equality of SPRs between two groups similarly as SCR described above. The Newcombe method will be used to construct its 95% confidence interval.

- Ratio of GMTs between treatment arms at Days 28, 56, 182, and 364 post-vaccination (adjusted for intergroup variation in baseline [pre-vaccination] titers). P-values may be generated for information and planning of future studies, but will not be adjusted for multiple comparisons. The following treatment group differences will be estimated to address secondary objectives.

- Ratio of GMTs between treatment arms at Days 0 and 28 post-vaccination using ANCOVA to compare the immunogenicity of Quad-NIV (60  $\mu$ g HA per each A and B strain) with 50  $\mu$ g of Matrix-M1 co-formulated prior to administration relative to a

similar formulation mixed in-clinic and also to 2 US-licensed active comparators include:

- Group B - qNIV CF A60/B60/M50 vs. Group A - qNIV Ref A60/B60/M50
- Group B - qNIV CF A60/B60/M50 vs. Group F - FHD3
- Group B - qNIV CF A60/B60/M50 vs. Group G - FBK4
- Ratio of GMTs between treatment arms at Days 0 and 28 post-vaccination using ANCOVA to compare the immunogenicity of Quad-NIV with increased B-antigen dose or increased Matrix-M1 dose relative to the “standard” co-formulated Quad-NIV formulation and also to 2 US-licensed active comparators include:
  - Group C - qNIV CF A60/B60/M75 vs. Group B - qNIV CF A60/B60/M50
  - Group C - qNIV CF A60/B60/M75 vs. Group F - FHD3
  - Group C - qNIV CF A60/B60/M75 vs. Group G - FBK4
  - Group D - qNIV CF A60/B90/M50 vs. Group B - qNIV CF A60/B60/M50
  - Group D - qNIV CF A60/B90/M50 vs. Group F - FHD3
  - Group D - qNIV CF A60/B90/M50 vs. Group G - FBK4
- Ratio of GMTs between treatment arms on Days 0, 28, 56, 182, and 364 using ANCOVA to evaluate the longevity of immune responses to Quad-NIV at different doses and formulations, with 1 of 2 different doses of Matrix-M1 adjuvant, and of 2 US-licensed comparators includes above comparisons and below comparison for each strain.
  - Group C - qNIV CF A60/B60/M75 vs. Group D - qNIV CF A60/B90/M50

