### 7.3 Analyses of Exploratory Objectives of Immunogenicity

The following exploratory antibody titers will be summarized using the same statistical approaches as the primary and secondary immunogenicity endpoints.

Microneutralization (MN) responses: Neutralizing antibody titers specific to vaccine-homologous A and B strain(s) and antigenically-drifted influenza strains, at Days 0 and 28 post-vaccination, as measured by a microneutralization assay. Note: additional time points may also be assessed. Derived/calculated endpoints based on these data will include:

- GMT – defined as the antilog of the mean of the log-transformed neutralizing titer for a given treatment group.
- GMR – defined as the ratio of post-vaccination and pre-vaccination neutralizing GMTs within the same treatment group (designated as GMRPost/Pre).
- SCR – defined as proportion of subjects in a given treatment group with either a baseline reciprocal titer of < lower limit of quantitation (LLOQ) and a post-vaccination reciprocal titer 4-fold higher than the LLOQ, or a baseline reciprocal titer of  $\geq$  LLOQ and a post-vaccination reciprocal titer  $\geq$  4-fold higher than the baseline titer. SCR and corresponding

2-sided exact binomial 95% CIs will be constructed by Clopper-Pearson method. Two-sided 95% CIs for the difference in SPRs between treatment groups will be based on the Newcombe hybrid score. Chi-Square p-value will be derived similarly as above.

- Ratio of GMTs between treatment arms at Day 28 post-vaccination (adjusted for intergroup variation in baseline [pre-vaccination] titers). Note: Same comparisons as HAI antibody titers between treatment arms will be conducted using ANCOVA.
- Proportions of Days 0 and 7 peripheral blood T cell isolates that secrete IL-2, IFN- $\gamma$ , and TNF- $\alpha$  cytokines following in vitro restimulation with HA in subjects selected for cellular immune response monitoring. Analysis of exploratory CMI response endpoints will be performed on approximately 189 subjects from 3 preselected sites (63 subjects per site) and results may be reported as an addendum to the main clinical study report.
- HAI titers, as described above. Proportion of subjects with  $\geq$  2-fold or  $\geq$  4-fold increases in HAI titers among those with low baseline titers (ie, lowest quintile) and corresponding 2-sided exact binomial 95% CIs will be constructed similarly by Clopper-Pearson method.

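### SAP 7.2: the sample code for the seroconversion rate names no event level while the code for the difference takes column 2, so under default PROC FREQ settings the two describe opposite events

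*SAP*

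**What the plan says.** SAP 7.2 defines the rate in terms of responders: "Seroconversion rate (SCR) – defined as proportion of subjects with either a baseline reciprocal (Day 0) titer of < 10" who then reach the stated post-vaccination titer, or who have the stated fold rise from a higher baseline. It then ties the calculation to code: "SCR and corresponding 2-sided exact binomial 95% CIs will be calculated using the Clopper-Pearson method with the following sample SAS code". That block, run by treatment, contains "tables seroconvind / binomial(exact) alpha=.05" and saves its result with "output out=out1 binomial". It has no LEVEL=, ORDER= or format.

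For the between-arm comparison, the same section gives a second block on the same variable: "tables trt*seroconvind / riskdiff (column=2 cl=(newcombe", with a chi-square request. Here an event level is named, namely the second column.

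The one-arm method carries over. For seroprotection (SPR), SAP 7.2 says "SPR and corresponding 2-sided exact binomial 95% CIs will be constructed similarly using the Clopper-Pearson method". For the 2-fold and 4-fold responders with low baseline titers, SAP 7.3 says "corresponding 2-sided exact binomial 95% CIs will be constructed similarly by Clopper-Pearson method". SAP 7.3 also cites Clopper-Pearson for the microneutralization (MN) SCR. Neither the SAP nor the protocol states how the responder indicators are coded.

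**The concern.** The two blocks are meant to describe one event, but only one of them says which level that event is. If the unlabelled block takes the other level, a results table could show per-arm rates for subjects who did not seroconvert beside a difference for subjects who did. The arms would then be ranked in opposite order by the two sets of figures.

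SCR and SPR are secondary endpoints at Days 28, 56, 182 and 364 (SAP 2.2.2). SAP 9 says the immunogenicity results beyond the primary comparison serve to choose a dose and formulation for the next study. The code would run without an error message, and if the production and checking programs both copied it they would agree on the wrong figure.

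**Working it through.** **Inputs**

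- Event intended: seroconversion (SAP 7.2 definition).
- One-arm code: no level named (SAP 7.2).
- Difference code: column 2 of the same variable (SAP 7.2).
- Coding of the variable: not stated in either document.
- Software assumption: with no LEVEL= option, PROC FREQ's BINOMIAL option analyses the first ordered level, and both blocks use default ordering. This is not in the documents, and SAS was not run.
- Sample size for illustration: 295 per arm, the per-protocol figure in SAP 9.
- The documents give no SCR, so there is no stated figure to reproduce. All rates below are assumed.

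**Step 1: which event each block describes**

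The one-arm block returns P(first level). The difference block returns a difference in P(second level). For a fixed order of arms X and Y:

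| Coding | One-arm block | Difference block |
|---|---|---|
| 0 = no, 1 = yes (or N/Y) | 1 − SCR | SCR_X − SCR_Y, correct |
| 1 = yes, 2 = no | SCR, correct | (1 − SCR_X) − (1 − SCR_Y) = −(SCR_X − SCR_Y), sign reversed |

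The two levels of a binary variable are complements, so no single coding makes both rows of output refer to seroconversion. The explicit request for column 2 suggests that the second level is the intended event, which makes the one-arm block the one to correct.

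**Step 2: illustration with two arms of 295**

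Assume 118/295 = 40.0% and 88/295 = 29.8% seroconvert.

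| | Arm X | Arm Y | Difference X − Y (Newcombe) |
|---|---|---|---|
| Event named correctly | 40.0% (34.4 to 45.8) | 29.8% (24.7 to 35.4) | +10.2 points (2.5 to 17.7) |
| As written, 0/1 coding | 177/295 = 60.0% (54.2 to 65.6) | 207/295 = 70.2% (64.6 to 75.3) | +10.2 points (2.5 to 17.7) |
| As written, responders sorted first | 40.0% (34.4 to 45.8) | 29.8% (24.7 to 35.4) | −10.2 points (−17.7 to −2.5) |

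In the second row the printed rates differ by 60.0 − 70.2 = −10.2 points while the printed difference is +10.2. The exact interval of the complement is the mirror image of the correct one: (1 − upper, 1 − lower).

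**Step 3: size**

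With 0/1 coding the printed rate is off by |1 − 2 × SCR|: 70 points at an SCR of 15%, 40 points at 30%, 20 points at 40% or 60%, and none at 50%.

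A rough range can be tied to the earlier trial. Protocol 1.8.1 gives fold rises of 1.9 to 3.2. Assume an SD of the log10 fold rise of 0.35 to 0.55 (in neither document) and normality, and apply the 4-fold rule alone: SCR = 1 − Φ((log10 4 − log10 fold rise)/SD).

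- Low end: (0.602 − 0.279)/0.35 = 0.92, so SCR is about 18%.
- High end: (0.602 − 0.505)/0.55 = 0.18, so SCR is about 43%.

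The complement would print as about 57% to 82%. This range is illustrative only. It uses Day 21 results, pools Tri-NIV and Fluzone HD, and ignores the separate rule for baseline titers below 10.

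**Step 4: groups with one level present**

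If every subject in a group responds, or none does, the only level present is also the first. The event analysed could then change from one group to the next. This is most likely in the small lowest-quintile subgroup of SAP 7.3.

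**The case against.** The strongest reply is that the prose governs and is unambiguous. SCR and SPR are defined as proportions of responders, Protocol 10.4.2 speaks of percentages with an immune response, and no text plans to report non-responders. The code is labelled as a sample and is plainly schematic. The one-arm block does not loop over strain or visit, the difference block suppresses printing and has no OUTPUT statement, and variable names change between blocks. A programmer has to rewrite it and may correct the level on the way. The first-level default is also outside the documents. All of this stands, and it limits the point to the code as written.

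Detection is also likelier in some places than in others. For SPR, Tri-NIV 180 µg GMTs of 106.2 to 209.8 (Protocol 1.8.1) with log10 SDs of 0.4 to 0.6 (SAP 9) imply, under normality, about 76% to 96%: (2.026 − 1.602)/0.6 = 0.71 and (2.322 − 1.602)/0.4 = 1.80. A complement of about 4% to 24% beside such GMTs would be conspicuous. For SCR, a complement of 57% to 82% would be less so, although the conflict with the difference and with the reverse cumulative distribution displays in SAP 7.3 would remain visible. The carry-over wording for SPR and the low-baseline proportions names the interval method rather than the code, so reuse of the code there is likely but not stated.

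A reader might infer that the trial will report non-seroconversion as SCR, or that the exact intervals have an error rate near 100%. The documents support neither. The first would require the sample code to be run unchanged against a clear definition. The second treats a wrong label as a property of the interval: the interval for the complement covers the complement correctly, and how far it lies from the true SCR depends on an SCR that the documents do not give.

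What the reply does not remove is that the SAP makes this code the stated means of calculation, and names the event in one block but not in the other.

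**Conclusion.** The point holds as an inconsistency between two stated analysis steps for secondary endpoints. Given the first-level default and default ordering, the blocks describe complementary events under any coding. Either the per-arm SCR and its interval are complements that contradict the prose definition and the between-arm difference, or the difference has the wrong sign. The size cannot be fixed from the documents: a true SCR of 30% would print as 70%, and the gap closes near 50%.

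A reader might also infer that the trial's main conclusion is at risk. It is not: the primary GMT ratio comes from the ANCOVA in SAP 7.1, which does not use this indicator, and the chi-square p-values do not depend on which level is called the event. Nor does either document set a decision rule on SCR or SPR for dose selection. The correction is worth making because the fault would run silently and costs little to remove.

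**What to change.** In SAP 7.2:

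- State that `seroconvind` and every other responder indicator is coded 1 = responder, 0 = non-responder.
- Name the event in the one-arm code, for example `binomial(exact level='1')`, and keep `column=2` in the difference code.
- Use the same convention wherever the code is reused: SPR, MN SCR, and the 2-fold and 4-fold proportions in the low-baseline subgroup.
- Require that groups with only one level present are still reported as n/n or 0/n responders with the exact interval. Naming the level does not by itself settle a group with no responders. For 0/n the limits are 0 and 1 − 0.025^(1/n), and for n/n they are 0.025^(1/n) and 1.

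As a check on any output, the difference between the two printed rates should equal the printed difference in size and sign.

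The cost is one option, a line on coding and a rule for one-level groups. No data, endpoint or interval method changes.

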Tri-NIV with Matrix-M1 adjuvant also proved to be immunogenic in subjects eliciting high HAI titers against both vaccine-homologous and drifted historic strains with a dose-response observed between the 45 and 180 µg total HA doses using an assay based on wild-type sequence virus-like particle (VLP) antigens. Notably, the 180 µg Tri-NIV dose induced higher HAI titers when compared to Fluzone HD against both vaccine-homologous and non-vaccine strains. Specifically, Day 21 HAI titers against A/Michigan (H1N1) among 180 µg Tri-NIV recipients were higher than Fluzone HD (ie, 209.8 vs 170.5, respectively) with a fold rise of 3.2 vs 2.6, respectively. A similar trend was noted with A/HongKong (H3N2) with HAI GMTs among 180 µg Tri-NIV recipients being higher than Fluzone HD (ie, 159.0 vs 115.7, respectively, with a fold rise of 2.7 vs 1.9, respectively). Responses against B/Brisbane were concluded to be comparable among 180 µg Tri-NIV recipients and Fluzone HD recipients (GMTs of 106.2 vs 108.6, respectively, and geometric mean ratio of titers pre and post vaccination [GMR] of 1.9 vs 2.0, respectively); it is also noted that the true HA content of B/Brisbane in the comparator was higher (~90 - 100 µg HA per dose), as measured by isotope dilution mass spectroscopy (IDMS) and single radial immunodiffusion (SRID), than that reported in the manufacturer's label (60 µg HA). All drift strains tested showed the same trend of higher HAI GMTs and GMRs with Tri-NIV at 180 µg total HA content compared to Fluzone HD [[Shinde 2018](#)].

A complete description of this clinical study is provided in the IB.

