In a previous study using the Tri-NIV formulation (tNIV-E-101), the observed strain-specific standard deviations of log10 HAI titers ranged from approximately 0.4 (B/Brisbane and A/Texas) to approximately 0.6 (A/Switzerland and A/Singapore). Table 6 summarizes power, unadjusted for multiple comparisons, for the primary objective to demonstrate superiority for pair-wise comparisons of the 2 treatment groups. Power calculations also accounted for a 5% attrition rate for the per-protocol population (295 evaluable subjects per treatment group) which is the primary analysis population for all immunogenicity endpoints. For each strain, this study

is designed to detect a 1.4-fold increase (40% increase) in GMTs with  $\geq 84\%$  power. For 2 strains, this study is designed to detect a 1.5-fold increase (50% increase) in GMTs with  $\geq 88\%$  power. For each strain, there will be 97.5% probability of demonstrating a non-inferior GMT for each comparison if 2 treatment groups have an equal GMT. Therefore, demonstrating a superiority against 2 strains with the true difference of 1.5-fold and a non-inferiority against 4 strains with the true difference of 1.0-fold, this study is designed to provide  $\geq 80\%$  power.

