## 12.2 Adjustments for Covariates

Comparison of GMTs between treatment groups will be adjusted for pre-vaccination titer.

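### Between-arm seroprotection comparisons ignore Day 0 titer: they are unbiased but less precise than they could be, and the SPR level needs its Day 0 value beside it

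*SAP*

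**What the plan says.** SAP 7.2 makes SPR a function of the post-vaccination titer alone: it is "defined as the proportion of subjects with a reciprocal HAI titer" of at least 40 on Days 28, 56, 182 and 364. Arms are compared by a chi-square test ("Chi-Square p-value will be derived for testing the equality of SPRs between two groups similarly as SCR described above") and a Newcombe interval, neither stratified.

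Baseline adjustment is specified for titers only. SAP 12.2 reads "Comparison of GMTs between treatment groups will be adjusted for pre-vaccination titer", and SAP 7.1 implements this by ANCOVA with log Day 0 titer. Randomization is stratified by site and 2017-18 vaccination history (SAP 1.2), not by titer, and no eligibility criterion in Protocol 5.1 or 5.2 refers to titer.

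On Day 0 SPR the texts differ. The opening sentence of SAP 7.2 includes Day 0 among the SPR time points, but its SPR bullet names only post-vaccination days. Protocol 10.4.2 defines SPR at any given time point and takes Day 0 as the reference. Neither document plans SPR by baseline status.

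**The concern.** Older adults, many vaccinated the season before, can carry HAI titers above 40 at entry. If most do, SPR is high before any injection, and a subject who starts above 40 can hardly change category. Two things follow. A high SPR at Day 28, or a maintained one at Day 364, says little about the vaccine unless the Day 0 rate stands next to it. And because Day 0 titer predicts Day 28 status, a comparison that ignores it carries avoidable variance.

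SPR is a secondary endpoint at every post-vaccination serology visit. SAP 9 says that the immunogenicity results other than the primary one serve the choice of dose and formulation for the next study. Imprecise SPR differences near the ceiling could make formulations look more alike than the data need leave them.

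**Working it through.** **1. The plan's own figure.** Neither document gives a baseline SPR or a power for SPR. The stated figure that uses the same SD is 84% power for a 1.4-fold GMT ratio, 295 per arm, SD 0.6 (SAP Table 6). Check: log10(1.4) = 0.1461; standard error 0.6 × √(2/295) = 0.0494; 0.1461/0.0494 − 1.96 = 1.00; Φ(1.00) = 84%. It reproduces.

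**2. Implied Day 0 titers.** Protocol 1.8.1 reports Day 21 GMTs and fold rises for Tri-NIV 180 µg versus Fluzone HD: A/Michigan "ie, 209.8 vs 170.5, respectively) with a fold rise of 3.2 vs 2.6, respectively"; A/HongKong "ie, 159.0 vs 115.7, respectively, with a fold rise of 2.7 vs 1.9, respectively"; B/Brisbane "GMTs of 106.2 vs 108.6, respectively, and geometric mean ratio of titers pre and post vaccination [GMR] of 1.9 vs 2.0, respectively". Day 0 GMT = Day 21 GMT / fold rise. On SD, SAP 9 says "the observed strain-specific standard deviations of log10 HAI titers ranged from approximately 0.4 (B/Brisbane and A/Texas) to approximately 0.6 (A/Switzerland and A/Singapore"; the time point is not given, so use at Day 0 is an assumption. With log-normal titers, P(Day 0 ≥ 40) = Φ(log10(GMT₀/40)/SD).

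| Strain, arm | Day 0 GMT | SD 0.4 | SD 0.5 | SD 0.6 |
|---|---|---|---|---|
| A/Michigan, Tri-NIV | 209.8/3.2 = 65.6 | 70.4% | 66.6% | 64.0% |
| A/Michigan, Fluzone HD | 170.5/2.6 = 65.6 | 70.4% | 66.6% | 64.0% |
| A/HongKong, Tri-NIV | 159.0/2.7 = 58.9 | 66.3% | 63.2% | 61.0% |
| A/HongKong, Fluzone HD | 115.7/1.9 = 60.9 | 67.6% | 64.2% | 62.0% |
| B/Brisbane, Tri-NIV | 106.2/1.9 = 55.9 | 64.2% | 61.4% | 59.6% |
| B/Brisbane, Fluzone HD | 108.6/2.0 = 54.3 | 63.0% | 60.5% | 58.8% |

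The range is about 59–70%. Allowing for 2-fold dilution steps raises it (64–77% with a quarter-dilution shift).

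**3. One setting in full.** Take Day 0 GMT 60, fold rise 1.9, SD 0.5, pre/post correlation 0.6 (assumed).
- Day 0: p₀ = Φ(log10(60/40)/0.5) = Φ(0.352) = 0.638.
- Day 28: p₁ = Φ(log10(114/40)/0.5) = Φ(0.910) = 0.819.
- Both ≥ 40 (bivariate normal): 0.589. Share of the Day 28 seroprotected already ≥ 40 at Day 0: 0.589/0.819 = 72%.
- Day 28 SPR given Day 0 ≥ 40: 0.589/0.638 = 0.923. Given < 40: (0.819 − 0.589)/0.362 = 0.635.
- Crude variance per subject: 0.819 × 0.181 = 0.148. Within strata: 0.638 × 0.923 × 0.077 + 0.362 × 0.635 × 0.365 = 0.129. Reduction: about 13%.

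**4. Range.** Over Day 0 GMT 55–60, fold rise 1.9–2.7, SD 0.4–0.6 and correlation 0.6–0.75, with equal arms, the reduction is 7–24%. As CI width this is 1 − √0.93 = 4% to 1 − √0.76 = 13%. For A/Michigan at 65.6 with fold rise 3.2, SD 0.4 and correlation 0.6, almost everyone passes 40 (p₁ = 0.964); the same formula gives 0.0329 against 0.0346, a reduction of only 5%. The already-seroprotected share is about 67–77% over the settings run.

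**5. What stratifying does to the effect.** In the step 3 setting, a 1.4-fold GMT advantage moves SPR by 11.7 points below 40 and by 3.8 points at or above it. Weighted, 0.362 × 11.7 + 0.638 × 3.8 = 6.7 points, which is also the crude difference. The Mantel-Haenszel difference targets the same quantity with less variance.

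**6. Power and bias by simulation.** Setting: 295 versus 147 subjects, A/HongKong GMTs, correlation 0.4–0.8, Monte Carlo error about ± 4 points; here Cochran-Mantel-Haenszel was run over Day 0 quintiles.
- SD 0.4: about 51% with the planned test, 53–60% stratified.
- SD 0.6: 35–37% planned, 40–52% stratified.
- The < 40 subset alone: 22–49%.
- With no true difference, the planned SPR and SCR tests gave mean differences of 0.0–0.2 points and one-direction error rates of 1.8–3.4% (nominal 2.5%).

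**The case against.** The case for leaving the plan alone is substantial.

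- **No bias.** A reader might infer that arm differences in SPR reflect prior immunity. They do not: randomization balances Day 0 titer in expectation, and the crude CI already allows for chance imbalance. This stands.
- **Seroconversion.** A reader might infer that SCR has the same defect. Its definition already uses the Day 0 titer (from < 10 to ≥ 40, or a 4-fold rise from ≥ 10). Only its test is unstratified, and stratifying would save about 2–7% of variance. This stands.
- **The ceiling remains.** Step 5 shows that stratifying does not enlarge the overall difference. The < 40 subset shows a larger difference but has less power than the whole-arm test. This stands.
- **Baseline is used elsewhere.** The plan has ANCOVA GMT ratios at every post-vaccination serology visit, within-arm GMRs, reverse cumulative distributions including Day 0, and an exploratory lowest-quintile analysis of fold rises. These carry most of the inference. None gives a more precise SPR difference, and the quintile covers 20% of subjects while some 30–41% may start below 40.
- **Day 0 SPR is planned in substance.** Protocol 10.4.2 covers it, so the SAP needs alignment, not a new analysis. This stands.
- **Borrowed inputs.** Of the three strains with prior GMTs, only A/Michigan is in this vaccine. The prior trial enrolled from age 60, and SD 0.6 belongs to strains with no reported baseline. This widens the uncertainty about size but does not remove the gain.

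**Conclusion.** The point holds as one of precision and presentation for SPR, at minor severity. The SPR comparison is valid as planned. It gives up roughly 7–24% of variance (as little as 5% where nearly all subjects pass 40) that a value already collected could recover. The level of SPR within an arm is mostly carried over from Day 0 and should not be read as vaccine response by itself.

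The size rests on log-normal titers, the prior trial's baselines carrying over, the quoted SDs applying at Day 0, and an assumed pre/post correlation of 0.6–0.75. The documents do not support a claim that the SPR or SCR comparisons are biased. SPR is secondary, Protocol 10.4.2 treats its p-values as informational, and the primary B versus E criterion rests on baseline-adjusted GMT ratios.

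**What to change.** In SAP 7.2:

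1. For each strain and post-vaccination visit, estimate the between-arm SPR difference stratified by Day 0 titer (< 40 vs ≥ 40), with Mantel-Haenszel weights, a stratified Newcombe 95% CI and a Cochran-Mantel-Haenszel p-value.
2. Keep the crude single-arm rates with Clopper-Pearson intervals.
3. Align the SPR bullet with Protocol 10.4.2 so that Day 0 SPR is tabulated beside Days 28, 56, 182 and 364.
4. Show SPR by Day 0 stratum descriptively, with a note that the < 40 subset alone has less power than the whole-arm comparison.
5. Treat stratification of SCR as optional.

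Record the departure from the unstratified interval of Protocol 10.4.2 in SAP 13, which now lists no changes. If it is adopted after unblinding, as the Version 2.0 changes in SAP 14.1 were, label it so.

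The cost is SAP wording and a few table columns. No new data are needed. Single-arm intervals in the < 40 stratum will be wide: with 147 evaluable subjects in an arm of 155 and 30–41% below 40, about 44–60 subjects.
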